5.3.1.2 Dose Fractionation

Patients will receive 3 fractions of radiation. The dose for all patients will be 18 Gy per fraction to the prescription line at the edge of the PTV (total dose = 54 Gy). All treatment must be completed within 16 days. The time between fractions is at the discretion of the investigator, but a minimum of 40 hours and a maximum of 8 days should separate each treatment. No more than 2 fractions will be delivered per week (7 consecutive days).

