5.3.1.3 Premedications

Although not mandatory, it is recommended that patients receive corticosteroid premedication (e.g., Dexamethasone 4 mg p.o. in a single dose, or equivalent) 15-60 minutes before each of the three treatments for the intended purpose of modulating immediate pulmonary inflammatory effects. Analgesic premedication to avoid general discomfort during long treatment durations also is recommended when appropriate.

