13.1.1 Blood Specimens for Biospecimen Banking and Correlative Science Studies

If consent is obtained, patients should have peripheral whole blood specimens collected by routine venipuncture at the following time points:

• Before surgery (Arm 1) or SBRT (Arm 2). Note: This specimen may be collected prior to the date of surgery or at the time of surgery (i.e., after induction of anesthesia per patient preference).

Two, 10 ml lavender top (K-EDTA) tubes and one 10 ml red top (no additive) tube. One tube of whole blood will be sent to the CSB for genomic DNA isolation. The remaining two tubes should be processed on site for plasma (K-EDTA) and serum (no additive) isolation, respectively. Aliquoted frozen plasma and serum will be shipped to the CSB.

• First post-operative visit at 4 weeks (Arm 1)

One 10 ml lavender top (K-EDTA) tubes and one 10 ml red top (no additive) tube. The two tubes should be processed on site for plasma (K-EDTA) and serum (no additive) isolation, respectively. Aliquoted frozen plasma and serum will be shipped to the CSB.

• Before (same day) final SBRT treatment (Arm 2)

One 10 ml lavender top (K-EDTA) tubes and one 10 ml red top (no additive) tube. The two tubes should be processed on site for plasma (K-EDTA) and serum (no additive) isolation, respectively. Aliquoted frozen plasma and serum will be shipped to the CSB.

• Every 6 months for 2 years, then yearly to 5 years (Arms 1 and 2) Note: No additional samples are required after disease progression/relapse.

One 10 ml lavender top (K-EDTA) tubes and one 10 ml red top (no additive) tube. The two tubes should be processed on site for plasma (K-EDTA) and serum (no additive) isolation, respectively. Aliquoted frozen plasma and serum will be shipped to the CSB.

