13.1.2 Tissue Specimens for Biospecimen Banking

If consent is obtained, snap frozen tissue specimens from the surgical resection (Arm 1) should be collected using the procedures described below.

Time Point	Material	Quantity	Kit	Shipping
Pre-intervention (Arms 1 and 2)	Whole blood Frozen plasma Frozen serum	1, 10 ml KEDTA tube 1, 10 ml KEDTA tube 1, 10 ml no additive tube	A	Spin, aliquot, and freeze serum and plasma Ship immediately to ACOSOG CSB
Post-op visit at 4 weeks (Arm 1)	Frozen plasma Frozen serum	1, 10 ml KEDTA tube 1, 10 ml no additive tube	С	Spin, aliquot, and freeze serum and plasma Hold or Ship immediately to ACOSOG CSB
Before final SBRT (same day) (Arm 2)	Frozen plasma Frozen serum	1, 10 ml KEDTA tube 1, 10 ml no additive tube	С	Spin, aliquot, and freeze serum and plasma Hold or Ship immediately to ACOSOG CSB
Every 6 mo. x 2 years Yearly until 5 years (Arms 1 and 2)	Frozen plasma Frozen serum	1, 10 ml KEDTA tube 1, 10 ml no additive tube	С	Spin, aliquot, and freeze serum and plasma Hold or Ship immediately to ACOSOG CSB

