14.2 Biomarkers of Tumor Recurrence and Treatment Toxicity

14.2.1 Study Design

All consenting patients will undergo collection of whole blood, serum, and plasma. For patients randomized to receive surgery, venous blood will be drawn pre- or intraoperatively and at the first post-op visit. For patients randomized to receive SBRT, venous blood will be drawn pretreatment, and immediately before the final SBRT treatment. Follow-up blood draws will be the same for all patients: q 6 months for 2 years, then yearly.

For Hypothesis A, blood markers will be correlated with time to tumor recurrence.

For Hypothesis B, blood based markers prior to, during and after treatment will be correlated with pulmonary complications (defined as grade \geq 3 events).

14.2.1 Hypothesis A: Blood based biomarkers, including osteopontin, will be able to predict which patients will be at high risk for recurrence by treatment with either SBRT or Surgery.

Introduction and Rationale

Resection alone is the standard of care for stage I NSCLC, but 27-55% of patients will develop loco-regional recurrence, [25-27] indicating a subgroup within this population which would benefit from additional therapies. In other solid tumors, biomarkers exist which aid in diagnosis, reliably define response to therapy, and serve as a marker for recurrence. The most clinically relevant of these include prostate specific antigen (PSA) in prostate cancer, carcinoembryonic antigen (CEA) in colon cancer[28] and cancer antigen 125 (CA-125) in ovarian cancer. No such marker exists for NSCLC. Hypermethylation of promoters, mutations in K-ras and p53, and protein biomarkers such as CEA, cytokeratin 19 fragment (CYFRA 21-1), plasma kallikrein B1, and neuron-specific enolase[29] have all been investigated, but currently lack clinical utility.

Osteopontin (OPN) is a multifunctional glyco-phosphoprotein originally described as a secreted protein from malignant epithelial cells.[30] It is identified in a remarkable range of normal and pathologic contexts,[31] and is an important adhesive bone matrix protein which plays a key role in the mediation of immune cell recruitment, wound healing, and tissue remodeling.[32, 33] OPN's diverse biologic functions relate to cell adhesion, migration, and invasion; and are mediated by integrin receptor binding and activation of its two highly preserved central binding domains.[34]

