Platelet-poor plasma will be obtained for cytokine and proteomic assays, serum samples will be used for metabolomics analysis. Buffy coat will be used for genomic studies. Plasma TGF- β 1 will be measured by molecular specific ELISA. The levels of other plasma cytokine will be measured by LINCOplex Kit (microsphere-based sandwich immunoassay) for the concentrations of proinflammatory cytokines, including G-CSF, IL-1 α , IL-1 β , IL-1 α , IL-6, IL-8, IP-10, MCP-1, MIP-1, TGF- α , and TNF- α) or other advanced kit with superior performance levels when they becomes available. RILT will be diagnosed and graded based on NCI's CTCAE. The plasma proteomes will be compared using a multiplexed quantitative proteomics approach involving ExacTag labeling, RP-HPLC and LC-ESI-MS/MS. Genomic studies such as single nucleotide polymorphism (SNP) studies will be performed using polymerase chain reaction (PCR) and allele specific primers. Since this is a prospective study, we anticipate advancement in experimental technology and preliminary results, other techniques and tests will also be applied if they are found them to be superior to the above stated ones.

Statistical Considerations

We recognize that almost all the data of the blood marker studies discussed above were related to RILT associated with conventionally fractionated radiation therapy. In this study, we hypothesized that severe pulmonary events from hypofractionated SBRT and surgical resection have a similar mechanism to that of RILT from 3DCRT. We will use logistic models to explore the relationship between grade \geq 3 pulmonary events and baseline levels of blood biomarkers of our interest (which may evolve with advances of technology and merging evidence) including (not limited to) TGF β 1, IL1, IL-6, IL-8 cytokine, SNPs of these cytokines and tPA, new proteomic makers prior to and during treatment. In addition, the Generalized Estimating Equation (GEE) method will be used to explore the relationship between treatment toxicities and marker levels measured during and after treatment. For proteomic analysis, variance components models will be used to identify the differential protein expression between patients with and without grade \geq 3 toxicity. Bioinformatic methodology may be applied for data analysis. As a secondary objective for toxicity study, we will also correlate blood based markers with grade \geq 3 non-pulmonary toxicities, which will also be defined by CTCAE.

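### The SBRT arm's only on-treatment blood sample is not ordered against that day's optional steroid, and the biomarker models name no steroid term

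*Combined protocol and SAP*

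**What the plan says.** **Timing of the sample.** Section 14.2.1 (Study Design) says of Arm 2: "venous blood will be drawn pretreatment, and immediately before the final SBRT treatment". The collection instructions are looser. Section 13.1.1 has "Before (same day) final SBRT treatment (Arm 2"), and the specimen table that follows Section 13.1.2 has "Before final SBRT (same day) (Arm 2"). The Study Calendar agrees with these two. None of them places the draw relative to premedication.

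**Premedication.** Section 5.3.1.3: "Although not mandatory, it is recommended that patients receive corticosteroid premedication". The timing and purpose are given as "15-60 minutes before each of the three treatments for the intended purpose of modulating immediate pulmonary inflammatory effects". Under Section 5.3.1.2, "a minimum of 40 hours and a maximum of 8 days should separate each treatment".

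**Use of the sample.** For Hypothesis B, "blood based markers prior to, during and after treatment will be correlated with pulmonary complications", where the outcome is a grade 3 or higher event. The Research Plan in Section 14.2.2 measures TGF-β1 by ELISA and uses a multiplex kit "for the concentrations of proinflammatory cytokines, including G-CSF" and IL-1, IL-6, IL-8 and TNF-α. Its Statistical Considerations relate levels during and after treatment to toxicity by GEE. No steroid covariate, stratum or sensitivity analysis is named.

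**The concern.** The protocol states that the premedication is meant to act on inflammation in the lung. The on-treatment sample is meant to capture inflammatory signals that predict severe lung events. If some patients are sampled shortly after a dose, some before it, and some without any premedication, part of the spread in marker levels reflects steroid exposure and draw order.

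At the least this is noise that dilutes a marker-toxicity association. If the choice to premedicate follows perceived lung risk, or if the steroid changes the risk of a severe event, steroid use could also distort the association. The background to Hypothesis B rests partly on signals during radiotherapy (TGF-β1 and IL-8 in Section 14.2.2), and the follow-up draws, which start at 6 months, cannot replace this sample.

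**Working it through.** The plan gives no figure on this point, so there is none to reproduce. The check is a comparison of texts, followed by an illustration on assumed inputs.

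**1. Possible orders on the day of fraction 3**

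| Patient | Draw directly ahead of the fraction (14.2.1) | Draw any time earlier that day (13.1.1, table, calendar) |
|---|---|---|
| Premedicated | Normally after that day's dose, which is due 15-60 minutes before the fraction | Before or after that day's dose |
| Not premedicated | No protocol premedication | No protocol premedication |

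For a patient premedicated throughout, two earlier doses precede the sample under either reading. By the fraction spacing, the nearer of them was given about 40 hours to 8 days before.

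**2. Reach.** The GEE draws on the final-fraction sample, four samples over 2 years (every 6 months) and three yearly samples to year 5: 1 + 4 + 3 = 8 at most. One of the eight is affected.

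**3. Information available.** Section 14.2.2 puts grade 3 or higher lung toxicity after SBRT at 10%, with 120 patients per arm for training and 80 for testing. Expected events: 0.10 × 120 = 12 and 0.10 × 80 = 8.

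**4. Dilution, if steroid use is unrelated to toxicity (illustration).** Let p be the share premedicated and d the steroid shift of the marker in SD units. The standardized contrast is multiplied by 1/√(1 + p(1−p)d²). The documents give neither p nor d.

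- *Milder inputs,* p = 25-75% and d = 0.25-1.0. Smallest effect (p = 0.25, d = 0.25): 1/√(1 + 0.1875 × 0.0625) = 0.99. Largest (p = 0.5, d = 1.0): 1/√1.25 = 0.89.
- *Stronger inputs,* p = 0.5 and a k-fold drop with log-SD s, so d = ln(k)/s. The slope per log unit is multiplied by s²/(s² + 0.25 ln(k)²), and the contrast per SD by its square root:

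| k | s | Per-unit slope | Per SD |
|---|---|---|---|
| 2 | 1.0 | 1/(1 + 0.120) = 0.89 | 0.94 |
| 2 | 0.6 | 0.36/(0.36 + 0.120) = 0.75 | 0.87 |
| 3 | 0.6 | 0.36/(0.36 + 0.302) = 0.54 | 0.74 |

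The per-SD column bears on detectability.

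**5. Power under the milder inputs.** A two-sample comparison of 12 against 108 patients stands in for the planned GEE, with an assumed true difference of 0.8 SD and two-sided 5%. The standard error is √(1/12 + 1/108) = 0.304, so z = 2.63 and power is 74.8%. With the dilution it falls to between 74.3% and 65.2%.

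**6. Distortion, if the steroid also lowers toxicity (illustration).** Take p = 0.5, 10% toxicity overall and an assumed relative risk of 0.5. Toxicity without steroid is 0.10/(0.5 × 0.5 + 0.5) = 0.133. The premedicated share is then 0.333 among patients with toxicity and 0.519 among those without. The spurious marker difference is d × (0.519 − 0.333), or 0.19 SD at d = 1.0. At relative risk 0.75 the shares are 0.429 and 0.508, giving 0.02 SD at d = 0.25. The range over both relative risks is 0.02-0.19 SD; with no effect on toxicity it is zero.

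**The case against.** The case for leaving the plan alone is substantial.

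- **The draw need not follow the dose.** A reader of Section 14.2.1 might infer that the steroid has just been given whenever this blood is taken. The collection instructions allow a pre-dose draw, so that is not established. The order is simply open.
- **The comparison group is not known to be steroid-free, and practice is not known to vary by site.** The documents neither describe nor exclude background steroid use in this population with poor lung function, and Section 5.3.1.3 speaks of patients and not of site policy.
- **Confounding is not shown.** A reader might infer that steroid use confounds the association. Section 5.3.1.3 claims only an effect on immediate inflammation, while Section 5.3.7 describes pneumonitis as arising weeks to months after treatment. Nothing says that a single dose per fraction alters grade 3 or higher events. Hypothesis B is also about prediction: if a steroid lowered both marker and toxicity, the unadjusted level could still predict.
- **Section 14.2.2 names no adjustment covariates at all,** and the case report forms are kept on a website outside these documents. They may already capture steroid use. Section 5.4.3.3 collects the daily radiation record, but does not say whether it shows premedication.
- **The aim is exploratory.** Specimens are optional, and Section 13 says that they are not integral to the trial design.

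These points limit the claim and its weight. They do not remove the gap: a plan that allows both draw orders, with an optional drug aimed at the process being measured, mixes pre-dose and post-dose samples if followed as written.

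**Conclusion.** The point holds as a minor design weakness. The visible plan does not order the final-fraction draw against premedication, ask for steroid exposure to be recorded with the sample, or account for it in the on-treatment models. The consequence is avoidable variation at one Arm 2 time point. Confounding is a possibility that depends on a link between steroid use and toxicity, which the documents do not establish.

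The size is unknown. The figures of 0.74-0.99 per SD and 0.02-0.19 SD rest wholly on assumed uptake, assumed marker shifts and an assumed relative risk. A reader might take the 0.54 per-unit slope to mean that nearly half of a real signal is lost. It does not: it is the most extreme of the assumed cases, and the same case retains 0.74 of the contrast per SD. Arm 1, the pretreatment marker models and the primary endpoint do not depend on this sample.

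**What to change.** Leave the premedication advice unchanged, and make three additions:

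1. Reconcile Section 14.2.1 with Section 13.1.1 and the specimen table by stating that the final-fraction blood is drawn before any premedication given that day.
2. Record steroid yes/no and time for each fraction, next to the draw time. Sections 13.2.1 to 13.2.3 already require the collection time on each tube, so the steroid entry is the missing part, unless the case report forms already hold it.
3. In Section 14.2.2, fit the models of on-treatment markers with steroid use as a covariate or stratum, at least as a sensitivity analysis beside the unadjusted model.

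The cost is a sentence of protocol text, one form item per fraction and one model term, with no extra visit or blood. With about 12 events in the training set, the extra term loses some precision, which is a reason to present it as a sensitivity analysis. The pre-dose draw removes only the same-day steroid effect. Any carry-over from fractions 1 and 2 can be handled only through the record and the model, and exposure not recorded at the time may not be recoverable later.

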2.2 Proximal Bronchial Tree Diagram (from RTOG 0236)

2.3 Staging Criteria

Patients will be staged according to the 7th edition of AJCC Cancer Staging Manual, 2010. See the staging reference in the Appendices.

3 Study Calendar

	Within 60	After	ARM	1 (SR)	ARM 2	(SBRT)				(From	B date o	OTH A f surge	RMS rv/end/	of SBR	T)			At time
days prior to reg. (except where noted)	reg. and before SBRT or surgery	At time of surgery	4 weeks post- op	Before final SBRT (same day)	4 weeks after SBRT	3 mo.	6 mo.	9 mo.	12 mo.	15 mo.	18 mo.	21 mo.	24 mo.	30 mo.	36 mo.	Yearly to 5 years	of disease relapse / PD	
Credentialing	x ¹																	
History & Physical, ECOG/Zubrod PS	Х			X		X	Х	Х	Х	Х	Х	Х	Х	Х	Х	Х	X	X
Pregnancy test	x ²																	
Tumor biopsy (and LN biopsy, if needed)	Х																	x ⁹
Pulmonary Function Tests	x ³						Х	Х		Х				Х				
PET/CT scan chest/upper abdomen	Х							Х		Х				Х		Х	Х	x ⁹
CT scan chest/upper abdomen				x ⁷			Х		Х		Х	Х	Х		Х			x ⁹
Adverse event assessment		X		Х		X	Х	Х	Х	Х								
Charlson Comorbidity Index		Х																
Blood specimen collection ⁴		x ⁵		X	X			Х		Х		Х		Х		Х	Х	
Tissue specimen collection ⁴			X															
EQ-5D, LCSS, LASA, UCSD SOB questionnaires		X		X		X	Х	X		X				Х				
QA submission to ITC		x ⁶		x ⁸		x ⁸												
Image submission to ITC																		x ⁹

1 Credentialing for surgery, brachytherapy, and SBRT may be completed any time prior to first registration. See Credentialing (Section 12).

2 For patients of childbearing potential.

3 Baseline PFTs are required within 90 days prior to registration. PFTs must include routine spirometry and DLCO. Arterial blood gases are not required but may be used as minor criteria for study enrollment. See Eligibility Criteria (Section 2.1).

4 Specimen collection is required for consenting patients only. See Biospecimen Collection (Section 13).

5 Pre-treatment blood specimen may be collected at the time of surgery for patients being treated on Arm 1.

6 Submission to ITC of the first patient's treatment plan is required prior to treatment for each type of SBRT system used at a site. See Quality Assurance Requirements (Section 5.4).

7 Post-implant CT scan is required for Arm 1 patients receiving brachytherapy.

8 See Quality Assurance Requirements (Section 5.4).

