5.3.7 Treatment Interruptions and Adverse Event Management Guidelines

In general, the need for treatment interruptions is rare in patients receiving SBRT. Interruptions should be avoided by preventative medical measures and nutritional, psychological, and emotional counseling. Treatment breaks, including indications, must be clearly documented in the treatment record.

Pneumonitis

Radiation pneumonitis is a subacute (weeks to months from treatment) inflammation of the end bronchioles and alveoli. **Note:** It is very important that a Radiation Oncologist participate in the care of the patient, as the clinical picture may be very similar to acute bacterial pneumonia, with fatigue, fever, shortness of breath, nonproductive cough, and a pulmonary infiltrate on chest x-ray. The infiltrate on chest x-ray should include the area treated to high dose, but may extend outside of these regions. The infiltrates may be characteristically "geometric" corresponding to the radiation portal, but may also be ill defined.

Patients reporting symptoms as above will be promptly evaluated and treated. Mild radiation pneumonitis may be treated with nonsteroidal anti-inflammatory agents or steroid inhalers. More significant pneumonitis will be treated with systemic steroids, bronchodilators, and pulmonary toilet. Supra- and concurrent infections should be treated with antibiotics. Consideration of prophylaxis of opportunistic infections should be considered in immunocompromised patients.

It is unlikely that symptomatic pneumonitis will occur during the weeks radiation is actually delivered to the patients. However, if a patient experiences pneumonitis before completing therapy, therapy will be put on hold until symptoms resolve.

When symptomatic pneumonitis resolves to grade 0, the treating physician will contact the RTOG Study Cochair for a decision to continue or terminate protocol therapy. All decisions by the RTOG Co-chair must be documented in the patient's chart.

Bronchial Injury (e.g., bronchial obstruction; bronchial stricture; bronchopleural fistula)

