op OPN (271±31) in NSCLC patients was significantly higher than in smokers (40 ± 2 , p=0.001). Pre-op OPN was similar in the NSCLC validation cohort (324 ± 20 , p=0.134). Post-op OPN (256 ± 21) measured at mean of 9.8 weeks (range 2-46) was significantly lower than pre-op (p=0.005). Time from surgery significantly impacted post-op OPN: OPN≤6 weeks post-op (303 ± 26) was higher than OPN>6 weeks post-op (177 ± 29) (p=0.003).

In two patients with documented recurrence (Figure 1), plasma OPN was elevated to greater than the postsurgery nadir at the time of recurrence. This provides preliminary evidence of a relationship between plasma OPN levels and NSCLC recurrence that warrants additional investigation. Although the utility of biomarker elevation alone as a trigger to initiate therapy is of questionable value, its utility in helping to determining recurrence with other clinical indicators has significant merit. Hence, plasma OPN levels are elevated in early stage NSCLC patients and are significantly reduced following resection. Peri-operative reductions in plasma OPN may serve as a marker for response to therapy.

recurrence had an accompanying rise in plasma OPN from their post-op nadir.

Research Plan

Plasma OPN level determination will be performed either via multiplex Luminex assay or by individual ELISA. The advantage of the luminex assay would be that multiple biomarkers could be evaluated in a longitudinal fashion and also serve as the same platform for translational Hypothesis B. The NYU Thoracic Laboratory is expert in both OPN ELISA as well as Luminex assays.

There will be roughly 200 patients per arm randomized for this trial, and it is expected that baseline samples will be collected from nearly 100% of the registered patients. We anticipate that follow-up samples will be available from 80 to 100% of the patients. Hence, it is anticipated that a training set of 120 patients in each arm will be used to predict those biomarkers, including OPN, which are associated with recurrence by radiologic and histologic criteria, and a test set of 80 patients will be used for further validation of the profile(s) discovered in the training set.

14.2.2 Hypothesis B: Blood based biomarkers, including TGF-β1, will be able to predict which patients will be at high risk for pulmonary complications by treatment with either SBRT or Surgery.

Introduction and Rationale

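### Hypothesis B relates post-treatment marker levels to grade ≥3 pulmonary events with no rule that the sample precede the event, so a marker raised by a complication could be reported as predicting it

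*Combined protocol and SAP*

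**What the plan says.** - **Aim.** The heading of Hypothesis B (section 14.2.2) says that blood markers "will be able to predict which patients will be at high risk for pulmonary complications by treatment with either SBRT or Surgery". Section 1.3.3 lists the same aim among the correlative objectives, worded as exploration.
- **Design.** Section 14.2.1 (Study Design) states that "blood based markers prior to, during and after treatment will be correlated with pulmonary complications", the complications being grade 3 or higher.
- **Models.** The statistical considerations under section 14.2.2 name three. A logistic model relates grade ≥3 pulmonary events to baseline marker levels, and its list includes new proteomic markers before and during treatment. The GEE method "will be used to explore the relationship between treatment toxicities and marker levels measured during and after treatment". Variance-components models compare protein expression in patients with and without grade ≥3 toxicity, with no sample time given.
- **Validation.** In each arm, 120 patients form the training set and 80 the test set, read blinded.
- **Draws (section 13.1.1).** Both arms are drawn before treatment. The SR arm is drawn again at the 4-week visit and the SBRT arm on the day of the last fraction, before it is given. Both arms are then drawn at 6, 12, 18, 24, 36, 48 and 60 months.
- **Events.** In the Study Calendar (section 3) the row "Adverse event assessment" is marked after treatment at 4 weeks and at 3, 6, 9 and 12 months. The table is broken in the extracted text, so this is a reading of it. Section 5.3.7 says: "Radiation pneumonitis is a subacute (weeks to months from treatment) inflammation of the end bronchioles and alveoli".

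No section requires the sample to precede the event, sets a landmark, lags the marker in the GEE, or keeps post-event samples out of the training and test sets.

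**The concern.** A predictor has to be measured before what it predicts. The candidate markers include inflammatory and profibrotic cytokines. Section 14.2.2 itself describes IL-6 as a mediator of the acute-phase response and IL-8 as a signal that draws neutrophils to inflamed tissue. A patient who had a lung infection or pneumonitis before the draw may have a raised level because of it. A model that ignores time order counts that level in favour of the marker.

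Splitting the sample does not protect against this. A test set guards against overfitting, and blinding guards against biased reading. Neither changes the order of event and sample, so the same artefact would recur in the 80 test patients and look like confirmation. At stake is the product of Hypothesis B: a marker put forward as identifying high-risk patients before treatment or early after it, when it may only register that the complication has occurred.

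**Working it through.** The plan states no power, error rate or effect size for Hypothesis B, so there is no figure to reproduce. The check has two parts.

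**1. Draws set against events**

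| Draw | What the documents say about events by then |
|---|---|
| Baseline, both arms | Before treatment |
| SBRT, before final fraction | Section 5.3.7 considers symptomatic pneumonitis during the radiation weeks unlikely, so the draw largely precedes it |
| SR, week 4 | About the end of the 30-day window in which Z4032 saw grade 3+ events in 29/114 = 25.4% (SR) and 33/109 = 30.3% (SR with brachytherapy); all adverse events, not only pulmonary (section 1.1) |
| Month 6, both arms | 3 of the 5 scheduled post-treatment assessments done (4 weeks, 3 and 6 months); 2 remain. First SBRT draw after the final fraction |
| Months 12 to 60 | 6 of the 7 common follow-up draws fall at or after the last scheduled assessment; 5 of 7 strictly after it |

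So the pre-treatment and on-treatment samples are in the right order, or nearly so. For the later ones the order varies by patient and the plan does not control it.

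**2. Illustration of size**

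Inputs from the plan: *n* = 120 (training set, one arm), and severe pulmonary events in 5–10% after SR and 10% after SBRT (section 14.2.2). Assumptions, not from the documents: the marker has no predictive value; a share *f* of events precedes the draw; an event raises the level at the draw by *d* SD; the test is a two-sided 0.05 comparison of patients with and without the event.

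With *k* events, the mean difference between the groups is *f·d*, and

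z = f·d / √(1/k + 1/(n − k)), chance of a false association = Φ(z − 1.96) + Φ(−z − 1.96).

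At 10% events, *k* = 12 and √(1/12 + 1/108) = 0.304. For *f* = 0.25 and *d* = 0.5: z = 0.125/0.304 = 0.41, giving 0.061 + 0.009 = 7%. For *f* = 1 and *d* = 1: z = 3.29, giving 91%.

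| Share of events before draw | *d* = 0.5 SD | *d* = 1 SD |
|---|---|---|
| 25% | 7% | 13% |
| 50% | 13% | 38% |
| 75% | 23% | 69% |
| 100% | 38% | 91% |

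At 5% events (*k* = 6) the range over the same shares is 6–22% for 0.5 SD and 9–67% for 1 SD. In the test set (*n* = 80, *k* = 8) it is 6–27% and 10–77%. The test set is thus exposed to the same bias.

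This models a single draw in a two-group comparison, not the planned GEE, and ignores the extra spread among cases when only some events precede the draw.

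**The case against.** The best defence is that the plan already holds a sound predictive analysis. The logistic model is listed first and uses baseline levels, with some markers taken during treatment. The GEE on later levels is described as exploring a relationship, not as prediction. The objective is exploratory and, under section 13, specimen collection is optional and not integral to the trial design. All of this stands, and it limits the point to the later samples. It does not remove it: the Study Design text places all sample times under a hypothesis worded as prediction, follows with discovery and validation sets, and does not say which analyses may support a predictive claim.

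Three stronger readings are tempting, and the documents do not support them.

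- *Most events have already happened by the time of the post-treatment draws.* The Z4032 figures count any adverse event regardless of attribution, and section 8.3.3 shows that common ones included urinary tract infection and atrial fibrillation. No total beyond 30 days is given. For SBRT, section 1.1 reports toxic deaths many months or years after treatment, so the share before month 6 is unknown.
- *Most post-treatment samples are post-event samples.* With severe pulmonary events in roughly 5–10% of patients, most patients have no such event for a sample to follow.
- *The plan will report the GEE as prediction.* It does not say so. The text leaves that open, which supports could, not would.

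Nor do the documents say how long these markers stay raised after a complication resolves. The 0.5 and 1 SD shifts are assumptions.

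**Conclusion.** The point holds in limited form. The plan relates post-treatment marker levels to grade ≥3 pulmonary events under a predictive hypothesis with no time-order rule, so reverse causation could pass as prediction and survive the training/test split. It affects the GEE on levels during and after treatment, chiefly through the later draws, and the proteomic comparison if that uses post-treatment samples. The baseline logistic analysis is not affected.

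The size cannot be fixed from the documents. Under the stated assumptions, with 120 patients and 10% events, the false-association rate lies between 7% and 91% against a nominal 5%. It is near nominal if few events precede the draw and the rise is modest, and large if most do and the rise is 1 SD. The consequence is confined to an exploratory correlative objective; the primary and secondary endpoints are untouched.

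**What to change.** In section 14.2, before any marker analysis:

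1. Base prediction claims, and the training/test validation, only on samples drawn before event onset: the baseline sample in both arms, and the SBRT sample before the final fraction in patients event-free at that draw.
2. Use any later sample only in a landmark analysis of patients free of a grade ≥3 pulmonary event at the draw, counting only events with later onset.
3. Apply the same rule to the GEE and the proteomic models, and state the sample time for the proteomic comparison.
4. Report post-event levels separately, as association only.
5. Confirm that the adverse event form records onset date. Section 8.1 says that events go on the form but not that onset is dated. If it is not, place the event in its interval between assessments.

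The cost is wording, with no new visits or samples. The downside is fewer usable events for post-treatment samples. Landmarks at 12 months and later would have very few, since no scheduled adverse event assessment follows, so those draws would serve mainly for description.
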